Research Protocol: A Comparative Study of the Advantages of Water-Separation Circumcision

Study Title: Comparative Evaluation of Hydrodissection circumcision vs. Traditional Circumcision Techniques: A Randomized Controlled Trial

1. Study Objective: The objective of this study is to compare the clinical outcomes and advantages of water-separation circumcision (Group A) versus two traditional circumcision techniques (Group B: "Subcutaneous Tissue Sparing "and Group C: "Non-Subcutaneous Tissue Sparing ") in male patients.

2. Background and Rationale: Circumcision is one of the most commonly performed surgical procedures globally. Several techniques exist, including those that preserve or remove subcutaneous tissues. A newer method, water-separation circumcision, is being introduced as a potential improvement. This study aims to evaluate its effectiveness in terms of complications, healing time, and patient satisfaction, comparing it with traditional circumcision techniques.

3. Study Design: This is a **prospective, randomized controlled trial** designed to evaluate the clinical outcomes of water-separation circumcision (Group A) compared to two traditional circumcision techniques (Group B and Group C).

4. Inclusion Criteria:

- ① Complies with the diagnostic criteria for phimosis, foreskin elongation, and related diseases in the "Chinese Expert Consensus on Phimosis, Foreskin related Diseases";
- ② Preoperative routine examination showed no abnormalities in coagulation, blood routine, electrocardiogram and other indicators;
- ③ No severe genital herpes, gonorrhea, syphilis, glans infection, etc.;
- ④ Complies with the indications for sleeve type circumcision;
- ⑤ The patient or family member is aware of the surgical plan and signs the informed consent form.

5. Exclusion Criteria:

- ① Patients with concomitant urethral malformations, such as hypospadias;
- ② Patients with combined inflammation of the penis, prior penile surgery, severe adhesions, buried penis, and short frenulum of the penis;
- ③ Exclude individuals with combined allergies or allergies to multiple medications;
- ④ Patients with severe physical illnesses such as heart and lung dysfunction who cannot tolerate surgery;

- ⑤ Individuals with cognitive impairments or mental abnormalities;
- ⑥ Diabetes with poor glycemic control;
- ⑦ Age >35 or Age<6.

6. Intervention Groups:

Group A (Hydrodissection circumcision): This group will undergo the water-separation circumcision technique, where water is used to separate the skin from the underlying tissues before performing the circumcision (HC).

Group B (Subcutaneous Tissue Sparing Circumcision):

This group will undergo a traditional circumcision procedure where the subcutaneous tissue is preserved, aiming for less scarring and quicker healing (sCC).

Group C (Non-Subcutaneous Tissue Sparing Circumcision):

This group will undergo the traditional circumcision procedure in which the subcutaneous tissue is not sparing (uCC).

7. Outcome Measures:

Primary Outcome Measure:

1. operation time

Operative time was calculated by timer.

[Time Frame: 1 day]

2. intraoperative bleeding

The amount of intraoperative bleeding is calculated by weighing gauze before and after operation. 1 milliliter is approximately equal to the weight of 1 gram.

[Time Frame: 1 day]

3. The healing time

The healing time was judged by the doctors based on the observation of the wound and inquiry of the patients during 7-25 days after surgery. We defined complete wound healing as the absence of a scab with a completely epithelialized and dry skin surface based on clinical assessment.

[Time Frame: 7-25 days]

4. Intra-operative pain

Intra-operative pain was graded immediately after the operation while the post-operation pain was graded at 1 week by NRS (Numeric Rating Scale). The scale typically ranges from 0 to 10. 0 indicates no pain, while 10 signifies the most severe pain imaginable.

[Time Frame: 1 day]

Secondary Outcome Measures:

5. other complications

incidence rate

[Time Frame: through study completion, an average of 1 year]

6. patient satisfaction

Patient satisfaction is divided into 5 levels: Extremely dissatisfied, Dissatisfied, Neutral, Satisfied, Extremely Satisfied.

[Time Frame: through study completion, an average of 1 year]

8. Sample Size Calculation:

Given an assumed type I error (α) of 0.05 and type II error (β) of 0.20, a power of 80% is desired to detect a significant difference in the primary outcome (complication rate). Using a conservative estimate based on previous studies of circumcision complication rates, a sample size of 96 patients (32 patients per group) will provide sufficient power to detect differences between the three techniques.

This sample size assumes a 10% dropout rate, so 96 patients will be recruited in total.

9. Randomization:

Randomization will be performed using a computer-generated randomization list, ensuring that each participant has an equal chance of being assigned to one of the three groups. Stratified randomization

will be used to ensure balance across demographic variables (e.g., age, baseline health status). Patients will be blinded to group assignment, and the surgical team will remain unaware of the group allocation to reduce bias.

10. Statistical Analysis:

Data will be analyzed using the **Statistical Package for the Social Sciences (SPSS)** software, version 26 (or newer). The following statistical methods will be applied:

Descriptive statistics (mean, standard deviation, frequency distributions) will be used for demographic data and outcome measures.

Chi-square tests will be used to compare categorical variables (e.g., complication rates between the three groups).

Analysis of variance (ANOVA) will be applied to compare continuous variables (e.g., healing time, pain scores) between groups.

If assumptions of normality are violated, **Kruskal-Wallis tests** (non-parametric version of ANOVA) will be used.

Post-hoc tests (e.g., Tukey's test) will be applied where significant differences are found in the ANOVA. **Kaplan-Meier survival analysis** will be used to assess time to healing (i.e., complete wound closure). **P-values of < 0.05** will be considered statistically

significant. **Confidence intervals (95%)** will be reported for all continuous outcomes.

11. Ethical Considerations: The study will be conducted in accordance with the **Declaration of Helsinki** and will be approved by the Chongqing Jiulongpo Hospital ethics committee. All patients will provide written informed consent prior to participation, and their rights, confidentiality, and well-being will be ensured throughout the study. The clinical trial will be registered in a public database.

12. Timeline:

Study start date: 2019-6-30

Study end date: 2024-2-07

Recruitment period: 3 months

Follow-up period: 1 year after surgery

13. Budget Considerations:

Personnel costs (surgeons, nurses, data managers):

1000 x 96=96000RMB

Materials and Equipment (surgical tools, sutures, bandages, anesthesia)

500 x 96=48000RMB

Statistical and software tools: 1000 RMB

Participant compensation for time and travel:

1000 X96=96000 RMB

Principal Investigator: [[name]]

Study Coordinators: [[name]]

Contact Information: [Department of Urology,

Peking University First Hospital, 86

[name]]

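### Bleeding is taken from gauze weight with no allowance for the water used only in Group A, so this outcome may not be comparable between arms

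*Protocol*

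**What the plan says.** Protocol Section 7 places intraoperative bleeding second among four primary outcomes. The measurement rule is "The amount of intraoperative bleeding is calculated by weighing gauze before and after operation", with the conversion "1 milliliter is approximately equal to the weight of 1 gram". Nothing further is said about which gauze is weighed, when the first weighing takes place, or how fluid other than blood is handled.

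Protocol Section 6 describes Group A as the technique "where water is used to separate the skin from the underlying tissues before performing the circumcision". The descriptions of Groups B and C contain no such step, and no water volume is given.

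Under Section 10, ANOVA "will be applied to compare continuous variables", with Kruskal-Wallis if normality fails and a post-hoc test such as Tukey's. No adjustment to the bleeding measurement appears there or elsewhere. Section 1 gives the objective as to "compare the clinical outcomes and advantages of water-separation circumcision" against the two traditional techniques.

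**The concern.** Gauze weight gain measures all absorbed fluid, not blood alone. That does little harm when other fluid is similar across arms. Here one arm's technique puts water into the field by design and the others, as described, do not.

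Because the water belongs to one treatment, random allocation cannot balance it. A test on the recorded values cannot separate it from blood either: a shift from water looks the same as a shift from bleeding. Nor can a later analysis plan repair it, because gauze not kept apart and volumes not written down in theatre cannot be recovered.

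At stake is the Group A comparison on a listed primary outcome. A real reduction in bleeding could be missed, or an excess reported that is partly or wholly water.

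**Working it through.** **What follows from the text alone.** For one patient,

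recorded bleeding (mL) = gauze weight after − gauze weight before (g) = blood + other absorbed fluid.

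At about 1 g per mL, each gram of hydrodissection water on weighed gauze adds about 1 mL of recorded bleeding. Sections 6 and 7 together confine this term to Group A. The plan states no bleeding mean, SD or expected difference, so it has no figure for this outcome to reproduce. The 32 per group (3 × 32 = 96) was set for complication rate.

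**How much water would matter, in SD units.** With 32 per group, a pairwise comparison has standard error √(2/32) = 0.25 SD. If true bleeding is equal and water shifts Group A by r SD, the chance of a significant two-sided difference at 0.05 is Φ(r/0.25 − 1.96) + Φ(−r/0.25 − 1.96):

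- r = 0.25: 0.17
- r = 0.5: 0.52
- r = 1.0: 0.98

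If Group A truly bleeds 1 SD less, the chance of showing it is Φ((1 − r)/0.25 − 1.96). It falls from 0.98 at r = 0 to 0.85, 0.52 and 0.025 at the same three shifts.

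**Illustration in mL.** None of these inputs is in the protocol: comparator mean 8 mL; SD 2 or 4 mL; gamma-distributed blood loss; exponential leak with mean 1 mL in Group A, capped at 5 mL of water used; 32 per group; 6,000 simulated trials per cell. A difference is declared if ANOVA gives p < 0.05 and Tukey separates A from B or C.

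| Scenario | SD 2 | SD 4 |
|---|---|---|
| No true difference, 1 mL mean leak: false excess in A | 44.9% | 13.1% |
| True 2 mL reduction, no leak: reduction declared | 98.3% | 49.8% |
| True 2 mL reduction, 1 mL mean leak: reduction declared | 47.2% | 14.7% |
| Same, half the leak caught on separate gauze | 84.7% | 30.3% |
| Same, 80% caught | 95.3% | 42.0% |

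With no leak and no true difference, a false excess is declared in 1.6% to 1.8%. At a 0.5 mL mean leak, the false excess is 13% (SD 2) or 5% (SD 4), and the true reduction is declared in 85% or 30%.

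**Analytic check.** For a fixed 1 mL shift in A, the squared deviations of the three means sum to (2/3)² + 2 × (1/3)² = 2/3. The noncentrality is 32 × (2/3)/SD², which is 5.33 for SD 2 and 1.33 for SD 4. The noncentral F with 2 and 93 df gives 0.517 and 0.159, in line with the simulation, which also requires a Tukey difference and uses a variable leak.

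**The case against.** A reader might infer that recorded bleeding in Group A is wrong and cannot be compared with the other arms. The protocol does not support that. It nowhere says that water reaches weighed gauze; the water may stay in tissue or leave with the excised skin. Section 6 puts the water step ahead of the circumcision, so a first weighing after that step, or gauze used only from incision, would fit the text and remove part of the problem. Water released at incision would still count. What stands is that the values may not be comparable.

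A reader might also infer that the rule could favour the new technique. As written, with all blood-bearing gauze weighed, it cannot: the added weight only raises Group A's value. The opposite error needs bloody gauze left unweighed, which Section 7 does not describe.

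The importance can fairly be questioned. Section 2 gives the aims as complications, healing time and satisfaction, Section 8 sizes the trial on complication rate, and bleeding is one of four primary outcomes. Every input to the mL illustration is assumed, so its range reflects the chosen ratio of leak to SD and says nothing about the actual leak in this trial. Other fluids could wet gauze in any arm, but the protocol describes none and so no difference between arms in them. These points limit the weight of the concern. They do not remove it, since Section 7 does fix a rule, and that rule makes no allowance for a fluid specific to one arm.

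**Conclusion.** The concern holds conditionally. Hydrodissection water on weighed gauze enters a listed primary outcome one for one in Group A only, and nothing in the design or analysis removes it. The mechanism follows directly from Sections 6 and 7; that it occurs, and how large it is, does not. The bias may be zero. If it is present and all blood-bearing gauze is weighed, it runs against Group A. On the SD scale, a mean carry-over of half an SD would already give about an even chance of a false pairwise difference with 32 per group. The change is worth making because it is cheap and the missing information cannot be recovered later, not because the outcome has been shown to be invalid.

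**What to change.** Amend the bleeding item in Section 7 as follows.

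1. Use the same gauze-weighing procedure in all three arms. In Group A, collect fluid from the water step, before incision, on separately marked gauze; weigh and record it apart.
2. Record the water volume used for each Group A patient.
3. Compare the arms on the bleeding gauze and, as a sensitivity analysis, on total gain (bleeding gauze plus water-step gauze).

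Treat a Group A reduction as robust only if it also holds on total gain. Without that condition, blood lost onto the water-step gauze would drop out of Group A's value: on the same assumptions, 1 mL of blood lost that way gives a false reduction in about 45% (SD 2) or 13% (SD 4) of trials.

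Report a Group A excess or a null result in full, with the recorded water volume and a statement that residual water leaking at incision could have contributed. Do not make it conditional on a lower bound of total gain minus water volume. With 5 mL of water, a 1 mL mean leak and no true difference, that bound shows a Group A reduction in 100% (SD 2) or 97% (SD 4) of trials, so it is close to uninformative.

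The cost is one or two extra lines on the operation record and one marked gauze set. The correction is partial, since water left in tissue may still leak at incision. The total-gain condition also makes a reduction harder to claim: total gain equals the measurement as now written if all gauze is weighed, so in the illustration a robust reduction could be declared in at most 47.2% or 14.7% of trials. Section 12 gives a study end date of 7 February 2024. If operations are already complete, steps 1 and 2 cannot be applied, and the point should be reported as a limitation of the bleeding outcome.

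### The only power statement names complication rate as the primary outcome, but Section 7 lists complications as secondary

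*Protocol*

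**What the plan says.** Section 7 of the protocol has four entries under its primary heading:

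- operation time, intraoperative bleeding (an amount from gauze weight) and intra-operative pain (an NRS score from 0 to 10), each marked "Time Frame: 1 day";
- healing time, marked "Time Frame: 7-25 days".

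Complications appear once, as "5. other complications", an incidence rate under the secondary heading, followed to study completion (about one year).

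Section 8 holds the protocol's only power statement: "a power of 80% is desired to detect a significant difference in the primary outcome (complication rate"). It sets alpha at 0.05, beta at 0.20 and 32 patients per group, and refers to complication rates in unspecified previous studies without giving any. It closes: "This sample size assumes a 10% dropout rate, so 96 patients will be recruited in total".

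Section 2 does not rank the outcomes: "This study aims to evaluate its effectiveness in terms of complications, healing time, and patient satisfaction". Section 10 assigns chi-square tests to complication rates. It says ANOVA "will be applied to compare continuous variables (e.g., healing time, pain scores) between groups", and that post-hoc tests such as Tukey's "will be applied where significant differences are found in the ANOVA".

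**The concern.** The outcome said to have fixed the trial size is not one that Section 7 makes primary, and the power statement covers none of the four that are. A reader cannot tell which result the trial was designed to decide, and may wrongly carry the 80% over to operation time or healing time. With two versions of the primary outcome in one protocol, either could be cited once results are known: a null result on the four listed primaries could be set aside in favour of complications, or the reverse.

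**Working it through.** **1. The sections side by side.**

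| Outcome | Section 7 | Section 8 |
|---|---|---|
| Operation time | primary | no power stated |
| Intraoperative bleeding (amount) | primary | no power stated |
| Healing time | primary | no power stated |
| Intra-operative pain (NRS) | primary | no power stated |
| Complications (incidence) | secondary | called primary; 80% power |

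Section 2 names complications, healing time and satisfaction as aims, which is one listed primary and both listed secondaries. Section 10 gives tests for both kinds of outcome and ranks neither. Nothing breaks the tie.

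**2. Can the 96 be reproduced?** No. Inputs given: alpha 0.05, power 80%, three groups, 10% dropout. Inputs missing: the complication rates or a difference between them. Only the dropout step can be checked: 96 × 0.9 = 86.4, and 86 / 0.9 = 95.6, which rounds up to 96. Per group, 32 × 0.9 = 28.8. So 96 can be read as an already inflated total, and the dropout sentence is not an error.

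**3. Complication rate, for scale only.** The rates below are assumptions; the protocol gives none. For a three-group chi-square test (2 df, alpha 0.05), the noncentrality is λ = n Σ(pᵢ − p̄)² / [p̄(1 − p̄)], with n per group.

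- 5/15/15%: p̄ = 0.1167. At n = 32, λ = 2.07 and power is 0.23; at n = 29, power is 0.21.
- 5/5/30%: p̄ = 0.1333. At n = 32, λ = 11.54 and power is 0.87; at n = 29, power is 0.83.

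Expected counts are small, so the approximation is slightly generous. Exact enumeration of the same test gives 0.21 and 0.85 at n = 32, and 0.18 and 0.81 at n = 29. Either way, 80% lies inside the range.

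**4. What the fixed size can detect on the listed primaries.** Each outcome is taken alone at 80% power. About 96 patients are used for the three 1-day outcomes, assuming all recruited are operated on, and about 86 for healing time after dropout.

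ANOVA: power = P[F′(2, N − 3; λ = N f²) > F crit], solved for f.

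| Alpha | N = 96 | N = 86 |
|---|---|---|
| 0.05 | f = 0.322 | f = 0.341 |
| 0.0125 (0.05/4, an assumed split) | f = 0.381 | f = 0.404 |

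As a check, 200,000 simulated trials at these four f values gave power between 0.797 and 0.801. At f = 0.322, N = 96 and alpha 0.0125, power is 0.614.

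Tukey-adjusted pairwise difference: noncentral t with noncentrality d√(n/2) and critical value q/√2 (2.38 for 32 per group, 2.39 for 29). At alpha 0.05, d = 0.81 SD with 32 per group and 0.85 SD with 29 per group.

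**The case against.** The strongest reply is that the word for other in item 5 implies that bleeding and pain already count as complications, so the parenthesis in Section 8 is loose shorthand for the listed primaries. This fails. Section 7 measures bleeding as an amount and pain as a score; neither is a rate, no event threshold or composite is defined, and operation time is not a complication on any reading. What stands is that, if complications become primary, the definition must say which events count.

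A second reply is that the numbers are unnecessary and partly rest on assumptions. Much of this stands. The contradiction is textual, the complication rates are assumed, and the chi-square approximation is slightly favourable at low counts. The alpha split is not in the protocol, and how to handle four primaries may be set out in an analysis plan. The detectable differences are also approximate: they assume roughly normal data, whereas Section 10 switches to Kruskal-Wallis if normality fails, adds Kaplan-Meier for healing time and uses Tukey only after a significant ANOVA. None of this touches the conflict over what is primary.

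A third reply is that an analysis plan could settle the matter. It could supply missing detail, but it would leave two incompatible statements standing in the protocol.

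**Conclusion.** The point holds and must be fixed. As written, the 80% power is attached to an outcome that Section 7 lists as secondary, and no power is stated for any of the four listed primaries. That conclusion rests on the text alone.

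It does not follow that 96 patients are too few, or that the 80% is wrong; without rates, neither can be judged. For the listed primaries, the fixed size has 80% power for fairly large effects: f about 0.32, or 0.81 SD between two groups, for the three 1-day outcomes, and f about 0.34, or 0.85 SD, for healing time. These figures assume approximate normality, each outcome tested alone at 0.05, and the protocol's 10% dropout applied to healing time only. If alpha were split evenly over four primaries, power at f = 0.32 with 96 patients would fall from 80% to 61%.

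**What to change.** Keep 96 patients and make Sections 7 and 8 name the same primary outcome or outcomes. The sponsor decides which, following what was documented before data were seen.

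**(i) If Section 7 stands.** Remove the complication rate and its 80% claim from Section 8. State instead, per outcome at alpha 0.05 and 80% power, what the fixed size can detect:

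- operation time, bleeding and intra-operative pain (about 96 patients): ANOVA f about 0.32, or a Tukey-adjusted pairwise difference of about 0.81 SD;
- healing time (about 86 evaluable): f about 0.34, or about 0.85 SD.

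Say that these are sensitivity figures for each outcome taken alone, that they do not themselves justify 96, and that they make no allowance for four primaries. Describe complications as a secondary outcome with no power claimed.

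**(ii) If complication rate is meant to be primary.** List and define it as primary in Section 7, including which events count, and say whether the four outcomes now listed stay primary. In Section 8, state the assumed rates and the difference that about 29 evaluable patients per group can detect.

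**Cost.** Wording only: Section 8 under (i), Sections 7 and 8 under (ii). No extra patients and no change to Section 10. The sponsor either gives up the 80% claim for complications or commits to stated rates.

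### Section 9 names baseline health status, which eligibility leaves little room to vary, as a stratification factor, but not the operating surgeon, on whom operation time and bleeding depend; surgeon is not in the planned ANOVA either.

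*Protocol*

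**What the plan says.** Protocol Section 9 describes a computer-generated list with stratified randomisation that "will be used to ensure balance across demographic variables (e.g., age, baseline health status"). It gives no categories for either factor, and it does not mention the surgeon.

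The eligibility rules bear on the second factor. Section 4, item 2 requires: "Preoperative routine examination showed no abnormalities in coagulation, blood routine, electrocardiogram and other indicators". Section 5 excludes "Patients with severe physical illnesses such as heart and lung dysfunction who cannot tolerate surgery" (item 4), cognitive impairment or mental abnormality (item 5), "Diabetes with poor glycemic control" (item 6) and "Age >35 or Age<6" (item 7).

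Section 7 lists operation time and intraoperative bleeding as the first two primary outcomes. On the first it says "Operative time was calculated by timer". Section 10 compares continuous outcomes between groups by ANOVA, or Kruskal-Wallis if normality fails, and names no other factor in the model.

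On who operates, the only text is the Section 13 budget line "Personnel costs (surgeons, nurses, data managers"). Section 2 says of the technique: "A newer method, water-separation circumcision, is being introduced as a potential improvement".

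**The concern.** A stratification factor is worth its place if it varies among the patients randomised and predicts the outcome. Baseline health status, as far as the protocol describes it, largely fails the first test, because eligibility has already removed most of its variation. The surgeon, if there is more than one, passes both tests for operation time and bleeding: operators differ in speed and haemostasis whatever the technique.

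Two things are at stake. In a single trial of 32 per arm, one arm may by chance receive clearly more of the faster surgeon's cases, and the planned ANOVA has no means of allowing for it. Differences between surgeons also stay in the residual variance, so the comparison of techniques is less precise than it could be.

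The stratification factors are built into the allocation list, so they must be settled before the list is generated. A later statistical analysis plan cannot supply them.

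**Working it through.** The protocol gives no figure on this point to reproduce. Its own inputs are 96 patients, 32 per arm, three arms, alpha 0.05 and 80% power (Section 8). Everything about surgeons below is an assumption.

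**1. What health status could balance.** Assume that 2% to 10% of eligible patients fall in a poorer-health stratum.
- In total: 96 × 0.02 = 1.9 to 96 × 0.10 = 9.6 patients.
- Per arm: 32 × 0.02 = 0.6 to 32 × 0.10 = 3.2 patients.

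The factor would balance almost nothing. Age, the other named factor, runs from 6 to 35 and keeps real variation.

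**2. Chance imbalance in surgeon share.** Assume two surgeons with 48 cases each, allocated to three arms of 32 without regard to surgeon.
- SD of the difference in share between two arms: √(2 × 0.5 × 0.5 / 32 × 96/95) = 0.126, about 12.5 percentage points.
- A gap of 25 points is 8 patients of 32. Counting over all allocations of 48 cases to three arms of 32 gives 6.1% for a given pair of arms, and 15.2% for at least one of the three pairs.
- With a caseload of about 30/70 (29 and 67 cases), the SD is about 11.6 points and the two probabilities are about 4% and 10%.
- With one surgeon there is nothing to balance.

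**3. What a 25-point gap does to one trial.** With two equally busy surgeons whose means differ by g (in SD units), surgeon explains g²/4 of the variance, so g = 2√R².
- R² = 0.20: g = 0.89, and the shift in the arm difference is 0.25 × 0.89 = 0.22 SD.
- R² = 0.40: g = 1.26, and the shift is 0.25 × 1.26 = 0.32 SD.

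**4. Power.** With 32 per arm and two-sided alpha 0.05, a pairwise t-test has 80% power at d = 0.711. Removing the surgeon variance gives an effective d of d/√(1 − R²).
- R² = 0.20: 0.711/√0.80 = 0.795, power 0.879.
- R² = 0.40: 0.711/√0.60 = 0.918, power 0.951.

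To see which step earns the gain, I simulated 64 patients in two arms, with two equally busy surgeons and d = 0.711, 40,000 trials per cell:

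| Design and analysis | R² = 0.20 | R² = 0.40 |
|---|---|---|
| No surgeon stratum, no adjustment | 80% | 80% |
| Surgeon stratum, no adjustment | 82% | 86% |
| No surgeon stratum, adjustment | 87–88% | 95% |
| Surgeon stratum and adjustment | 87–88% | 95% |

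The adjustment does nearly all the work. The stratum keeps the arms comparable on surgeon within the one trial that is run, but adds almost no power once surgeon is in the model.

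**The case against.** Several objections have force.

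- **The list of factors is open.** Both factors follow an *e.g.*, so a reader should not infer that the protocol has fixed on health status or ruled out others. That stands. But the list is of demographic variables, a term that does not reach the operator, so the open wording does not bring surgeon in.
- **Health status is not strictly constant.** Controlled diabetes and milder conditions are not excluded by name, and the term is undefined. That stands: little variation is an inference from the criteria, not a stated fact. A weak stratum also does little harm; its cost is the place it takes.
- **Several surgeons are not documented.** The plural in a budget line that lists staff categories is the only hint. That stands, and it makes the stratum conditional on there being more than one.
- **Chance imbalance is not bias.** A reader might infer that omitting surgeon biases the trial. Under randomisation, chance imbalance adds variance, which the unadjusted standard error already reflects. Systematic channelling of one technique to one surgeon would bias the comparison, but the protocol describes no such assignment.
- **Learning curve.** A reader might also infer that Group A contains the surgeons' first hydrodissection cases and so looks slower than it should. Section 2 describes the method as new; it says nothing of these surgeons' prior caseload, so no size can be put on such an effect. A surgeon stratum would not remove it either, since every Group A case is a hydrodissection case.
- **Adjustment can be left to the statistical analysis plan.** In part that is so. The stratum, the prior assignment of surgeon and the spread of each surgeon over all arms cannot be.

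**Conclusion.** The point holds as a design improvement. It is not a contradiction in the protocol and does not invalidate the randomisation. Section 9 names a factor with little left to balance and omits the one most directly tied to the first two listed primary outcomes.

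Its size depends on the number of surgeons. With two, chance gaps of 25 points or more arise somewhere among the three arms in about 10% to 15% of allocations, depending on caseload split. Analysing by surgeon raises an assumed 80% power to about 87% at 20% of variance explained and 95% at 40%. That 80% is a reference level only, because Section 8 sizes the trial on complication rate and gives no effect size for operation time or bleeding. If one surgeon performs every operation, the stratification part falls away.

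**What to change.** State in the protocol how many surgeons operate and whether each performs all three techniques. If there is more than one:

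1. In Section 9, replace baseline health status with operating surgeon as a stratification factor, keep age, and give the categories of each. With, for example, two surgeons and two age bands there are four strata averaging 96/4 = 24 patients, which is workable.
2. Assign the surgeon before randomisation, and have each surgeon operate in all three arms.
3. In Section 10, include surgeon as a factor in the analysis of operation time and bleeding. This step brings the gain in precision; a stratum without it forgoes most of that gain.

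As a separate and secondary point, record each surgeon's running count of hydrodissection cases, including those before the trial, and report a sensitivity analysis of A versus B and A versus C without each surgeon's earliest cases. This is useful even with a single surgeon.

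The cost is one changed stratum in the allocation list and two items on the operation record (surgeon and case count). No extra patients are needed. The downside is practical: the surgeon must be settled before allocation, which restricts theatre scheduling somewhat.
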